Study Description	This is a retrospective analysis of the presence of chromosomal rearrangements involving MYC, BCL2 and BCL6 genes by FISH in a retrospective, single-center series of large B-cell lymphomas, in order to allow a better classifications of these cases according to the current WHO 2017 classification. If this evaluation will be confirmed as a reliable method to reclassify in different groups the evaluated tumors, it can be subsequently routinely apply to indicate the best treatment approaches in this high-risk setting of patients with a significant impact on patients' morbidity and mortality, and also on the health system and related costs.	
	Primary	Secondary
Objectives	
 1. To re-classify retrospective series of large B-cell lymphomas (LBCL) according to the current WHO 2017 classification by using FISH for the detection of MYC, BCL2 and BCL6 rearrangements. 2. To establish the association between re-classification of LBCL using FISH for the detection of MYC, BCL2 and 	
 1. To establish the association between re-classification of LBCL using FISH for the detection of MYC, BCL2 and BCL6 rearrangements and patients' outcomes. 2. To establish the association between re-classification of LBCL and risk of relapse. 3. To demonstrate that re-classification of LBCL exploiting FISH for the detection of MYC,

	BCL6 rearrangements and response to therapy.	BCL2 and BCL6 rearrangements is a reliable tool to support treatment decision plan. 4. To complete IHC analysis for further and/or novel pattern of antigen expression in HGBL. 5. To estimate the prevalence of MYC, BCL2 and BCL6 rearrangements/ amplifications detected by FISH in LBCL
Study Population	Adult subjects (> 18 years old) of any age and gender affected by large B-cell lymphoma. We expect to enroll around 555 subjects.	

	
Third, original slides will be reviewed and re-classified according to present WHO (2017) classification of lymphomas. Given that it is expected that a brand-new Classification will be shortly released in the forthcoming months by WHO, it is likely that additional diagnostic criteria will be further included within the central pathology review. Each DLBCL case will be stained, whenever not previously evaluated, with CD10, bcl-6 and MUM-1 antibodies and their respective secondary antibodies using an automated immunostainer. Staining data will be interpreted semiquantitatively. According to immunohistochemical results, each case will be further classified following to Hans' algorithm criteria. Each case will be also evaluated for c-MYC immunoreactivity and will be considered positive whenever more than 40% of cells will be stained for this marker. The correlation with FISH results will enable to select the actual high grade B cell lymphomas, which will be matched with clinical parameters and therapeutic responses.
 
FISH
 
Interphase Fluorescence In Situ Hybridization (I-FISH) for detection of MYC, BCL2 and BCL6 rearrangements will be performed on the previously histologically reviewed large B-cell lymphoma cases. A “split-apart” FISH approach will be used: the chosen probes for each gene of interest consist of two direct labelled gene locus regions (green and orange), hybridizing distal and proximal to the gene breakpoint and separation/fusion of the two signals will indicate presence/absence of the rearrangements. Three 4 µm tissue sections will be prepared for each sample, they will be pretreated according to the Zytolight FISH-Tissue Implementation Kit protocol (Zytovision, GmbH). Hybridization will be then carried out overnight on a Thermobrite hybridizer (Euroclone), using the Zytolight SPEC MYC Dual Color Break Apart Probe, Zytolight SPEC BCL2 Dual Color Break Apart Probe, Zytolight SPEC BCL6 Dual Color Break Apart Probe, following the manufacturer protocol; the next day, after unbound probes are removed by stringency washing steps, the slides will be counterstained with DAPI. Hybridized probes will be visualized using a fluorescence microscope (AxioImager Z2, Zeiss) equipped with excitation and emission filters specific for the fluorochromes by which the FISH probes are directly labeled. FISH semiautomatic analysis will be performed using the Metafer4 software (Metasystems): FISH signals will be counted in 200 interphase nuclei from at least 4 to 8 areas selected for well-preserved cellular and nuclear morphology to ensure representative sampling and to avoid nuclear truncation artifacts; a signal split, which indicates gene rearrangement, will be counted when the distance between splitted green and orange signals is ≥ 2 of the estimated signal diameter. The already defined laboratory cutoff for gene rearrangements will be used (2% for all the used probes).

--	--

	Results will be summarized for each case and reported to the pathologist.
Planned Study Periods	Duration of the Enrollment period: 1 year Duration of the retrospective Follow-up: NA Duration of total study period: 1 year

ABBREVIATIONS AND DEFINITIONS

Abbreviations

BL	Burkitt lymphoma
CR	complete remission
DLBCL	diffuse large B-cell lymphoma
DOT	Duration of response
FISH	fluorescent in situ hybridization
HGBL	High-grade B-cell Lymphoma
IC	Informed Consent
I-FISH	Interphase Fluorescence In Situ Hybridization
IHC	immunohistochemistry
OS	Overall Survival
PFS	Progression-free Survival
PR	partial response

BACKGROUND

The 2017 WHO classification introduced the new clinical entity “High-grade B-cell Lymphoma” (HGBL), including large B-cell lymphomas with chromosomal rearrangements involving MYC gene (region 8q24) and BCL2 gene (region 18q21) (so called “double hit lymphoma”, representing 60% of HGBL) and/or BCL6 (region 3q27) (also called “triple hit lymphoma”, representing 20% of HGBL), identified by means of fluorescent in situ hybridization (FISH) and/or conventional cytogenetic analysis. HGBL replaced the old WHO 2008 category of ‘unclassifiable B-cell lymphoma with features intermediate between diffuse large B-cell lymphoma and BL’ and encompasses also diffuse large B-cell lymphoma (DLBCL) by morphology harboring MYC and BCL-2 and/or BCL-6 rearrangements.

Clinically, HGBL are characterized by adverse prognosis and poor response to standard treatments, such as R-CHOP regimen, with a median OS of 12 months or less. The role of

intensified chemo-immunotherapy approaches has been investigated. Promising results emerged when treating patients with R-DA-EPOCH regimen, together with adequate CNS prophylaxis. [Petricch AM, Blood 2014]. Excellent efficacy and safety results were also reported in a multicenter phase II trial addressing a dose-dense, short-term therapy in HIV-positive patients diagnosed with high-risk BL or HGBL with MYC rearrangements [Ferreri et al. BJH 2021]. In the last decades, the “CARMEN” regimen was adopted at our institution and at several Italian Centers also for the treatment of HIV-negative patients diagnosed with high-risk DLBCL as well as B-cell lymphoma unclassifiable with features intermediate between DLBCL and BL with alterations of c-MYC. A retrospective series of 63 HIV-negative and –positive patients (22 HGBL) confirmed good tolerability and efficacy: after induction, 18 (82%) HGBL patients achieved a response, which was CR in 10 (45%) patients. At a median follow-up of 54 (2-131) months, the 5-year PFS and OS among HGBL were 67% and 66%, respectively. HIV seropositivity did not modify outcome.

Although FISH represents the gold standard for detection of MYC, BCL2 and BCL6 rearrangements, it is not routinely recommended in all cases at diagnosis. Indeed, a consensus has not yet been reached to provide specific guidelines as to which LBCL should be evaluated. Some believe that all DLBCL should have genetic studies for the detection of the three genes rearrangements, whereas others would limit them, for example, to cases with a GCB phenotype and/or high-grade morphology or to cases with >40% MYC+ cells in immunohistochemistry (IHC). In particular, at our institution, FISH for MYC is considered when MYC expression by IHC is >40%, and FISH for BCL-2 and BCL-6 are performed only when FISH for MYC is positive. However, since the presence MYC and BCL2 and/or BCL6 rearrangements is not invariably associated with IHC overexpression, the current diagnostic approach could have underestimated the real incidence of HGBL leading to the undertreatment of these patients.

RATIONALE

We propose to retrospectively analyze the presence of chromosomal rearrangements involving MYC, BCL2 and BCL6 genes by FISH in a retrospective, single-center series of large B-cell lymphomas, in order to allow a better classifications of these cases according to the current WHO 2017 classification. If this evaluation will be confirmed as a reliable method to reclassify in different groups the evaluated tumors, it can be subsequently

routinely apply to indicate the best treatment approaches in this high-risk setting of patients with a significant impact on patients' morbidity and mortality, and also on the health system and related costs. Moreover, this study could give important information about the real incidence and predictive value of MYC, BCL2 and BCL6 rearrangements.

OBJECTIVES

Primary objectives:

1. To re-classify retrospective series of large B-cell lymphomas (LBCL) according to the current WHO 2017 classification by using FISH for the detection of MYC, BCL2 and BCL6 rearrangements.
2. To establish the association between re-classification of LBCL using FISH for the detection of MYC, BCL2 and BCL6 rearrangements and survival.

Secondary objectives:

1. To establish the association between re-classification of LBCL using FISH for the detection of MYC, BCL2 and BCL6 rearrangements and patients' response to treatments.
2. To establish the association between re-classification of LBCL and risk of relapse.
3. To demonstrate that re-classification of LBCL exploiting FISH for the detection of MYC, BCL2 and BCL6 rearrangements is a reliable tool to support treatment decision plan.
4. To complete IHC analysis for further and/or novel pattern of antigen expression in HGBL.
5. To estimate the prevalence of MYC, BCL2 and BCL6 rearrangements/amplifications detected by FISH in LBCL
6. To describe the main treatment patterns according to disease characteristics.

THERAPEUTIC OUTCOME

Primary outcome:

1. Overall Survival (OS)

Secondary outcome:

1. Progression-free Survival (PFS)
2. Overall Response Rate (ORR; partial response [PR] + complete remission [CR])
3. Duration of response (DOR; partial response [PR] + complete remission [CR])
4. Relapse rates and patterns
5. Incidence of MYC, BCL2 and BCL6 rearrangements in LBCL

STUDY DESIGN

Single center, retrospective observational, pharmacological and of molecular characterization study.

Study duration 1 year

STUDY POPULATION

Adult subjects (> 18 years old) of any age and gender affected by large B-cell lymphomas.

Inclusion Criteria:

- Histologically-confirmed diagnosis of LBCL (i.e., DLBCL, HGBCL, unclassifiable B-cell lymphoma with features intermediate between DLBCL and BL), or aggressive B-cell lymphomas with blastoid morphology (excluding blastoid variant of mantle cell lymphoma and lymphoblastic lymphoma)
- Histopathological diagnosis performed between 2000 and 2019.
- HIV sero-negativity
- Age ≥ 18
- Treatment with R-CHOP or other intensified polychemotherapy regimen
- Availability of adequate histopathological samples at diagnosis for FISH analysis
- Availability of clinical records and outcomes data

Exclusion criteria

- Histologic diagnosis other than DLBCL or unclassifiable B-cell lymphoma with features intermediate between DLBCL and BL

METHODS

Diagnostic tissue samples of patients who fulfil selection criteria for enrolment into the study will undergo local histopathological revision and analysis of chromosomal rearrangements involving MYC, BCL2 and BCL6 genes by FISH. Moreover, completion of IHC analysis for further and/or novel pattern of antigen expression in HGBL will be performed.

Treatments: anthracycline-based combinations followed or not by involved-field radiotherapy

Assignment of Subject Identification

The participants will be assigned a unique trial specific number and will henceforth be identified by that number in the database.

Data Collection

The data of all patients enrolled in the study will be collected from clinical folders and source documents (e.g., hospital records; clinical and office charts; laboratory notes etc.) and registered in the database as described in the following paragraphs.

Histopathology and Immunohistochemistry

Nodal and extra nodal tissues with a diagnosis of DLBCL, lymphomas with intermediate features between Burkitt lymphoma and DLBCL, Burkitt-like lymphomas, and atypical Burkitt lymphomas will be searched within the files of Pathology Unit at San Raffaele Scientific Institute. The selection process will rely on sequential steps. First, we will retrieve archival cases from our tissue repository placed in the Pathology unit of the OSR. Second, we will carefully consider only tissue blocks showing enough material to allow completion of immunohistochemistry and FISH analyses. Third, original slides will be reviewed and re-classified according to present WHO (2017) classification of lymphomas. Given that it is expected that a brand-new Classification will be shortly released in the forthcoming months by WHO, it is likely that additional diagnostic criteria will be further included within the central pathology review.

Each DLBCL case will be stained, whenever not previously evaluated, with CD10, bcl-6 and MUM-1 antibodies and their respective secondary antibodies using an automated immunostainer. Staining data will be interpreted semiquantitatively. According to immunohistochemical results, each case will be further classified following to Hans' algorithm criteria. Each case will be also evaluated for c-MYC immunoreactivity and will be considered positive whenever more than 40% of cells will be stained for this marker. The correlation with FISH results will enable to select the actual high grade B cell lymphomas, which will be matched with clinical parameters and therapeutic responses.

FISH

Interphase Fluorescence In Situ Hybridization (I-FISH) for detection of MYC, BCL2 and BCL6 rearrangements will be performed on the previously histologically reviewed large B-cell lymphoma cases. A "split-apart" FISH approach will be used: the chosen probes for each gene of interest consist of two direct labelled gene locus regions (green and orange), hybridizing distal and proximal to the gene breakpoint and separation/fusion of the two signals will indicate presence/absence of the rearrangements. Three 4 μ m tissue sections will be prepared for each sample, they will be pretreated according to the Zytolight FISH-Tissue Implementation Kit protocol (Zytovision, GmbH). Hybridization will be then carried out overnight on a Thermobrite hybridizer (Euroclone), using the Zytolight SPEC MYC Dual Color Break Apart Probe, Zytolight SPEC BCL2 Dual Color Break Apart Probe, Zytolight SPEC BCL6 Dual Color Break Apart Probe, following the manufacturer protocol; the next day, after unbound probes are removed by stringency washing steps, the slides will be counterstained with DAPI. Hybridized probes will be visualized using a fluorescence microscope (AxioImager Z2, Zeiss) equipped with excitation and emission filters specific for the fluorochromes by which the FISH probes are directly labeled. FISH semiautomatic analysis will be performed using the Metafer4 software (Metasystems): FISH signals will be counted in 200 interphase nuclei from at least 4 to 8 areas selected for well-preserved cellular and nuclear morphology to ensure representative sampling and to avoid nuclear truncation artifacts; a signal split, which indicates gene rearrangement, will be counted when the distance between splitted green and orange signals is ≥ 2 of the estimated signal diameter. The already defined laboratory cutoff for gene rearrangements will be used (2%

for all the used probes). Results will be summarized for each case and reported to the pathologist.

STUDY VARIABLES

Conventional anographic variables, findings of histopathological diagnosis, results of IHC and FISH analyses, staging, therapeutic management and outcome will be considered.

DATA MANAGEMENT

Data Recording and Record-Keeping

All relevant data collected during the study for all of the patients enrolled in the study shall be entered in a database (password protected excel) from source documents (e.g., hospital records; clinical and office charts; laboratory notes etc.) by the responsible investigator or someone authorized by the investigator in a timely manner (as soon as possible after the information is collected) to ensure that they are clear, complete and correct.

On all trial-specific documents, other than the signed consent, the participant will be referred to by the trial participant number/code, not by name.

The investigator shall arrange for the retention of patient files, other source data, and the Trial Master File for at least 7 years after the completion or discontinuation of the study.

Data Protection

The confidentiality of participant data, including, but not limited to forms, records and samples and participant privacy will be maintained according to the GDPR (UE) 2016/679.

The trial staff will ensure that the participants' anonymity is maintained. The participants will be identified only by initials and a Patient ID number on the ICF and the electronic database.

All documents will be stored securely and only accessible by trial staff and authorized personnel.

Data anonymization

Since this is a retrospective study without ad hoc informed consent, in order to ensure anonymity, the following procedure will be followed for all data of all subjects:

the assigned patient ID will not be related to the identification code present in the patient's clinical material; this will be guaranteed with the following procedures:

- A patient code will be associated with the clinical material (nominal);

- The code will be transcribed in a second document and associated with a second code obtained by randomization (called "Patient ID");
- The patient ID will then be reported in the CRF and the intermediate document will be destroyed at termination of data collection.

At the end of this process and in the continuation of the study, patient data will be treated completely anonymously.

STATISTICAL CONSIDERATIONS AND ANALYSIS PLAN

Clinical characteristics and response rates of the therapeutic subgroups will be compared using the α_2 test or Fisher exact test for categorical variables, according to the sample size. Factors potentially conditioning outcome will be assessed by α_2 test and logistic regression. Survival curves will be generated by the Kaplan-Meier method. Overall survival (OS) will be calculated from the date of pathologic diagnosis to death or to the last date of follow-up, while progression-free survival (PFS) will be calculated from the first day of treatment to relapse, progression or death, or to the last date of follow-up. Survival rates will be reported as 2-year OS and 95% CI. Impact on survival of clinical and therapeutic variables will be evaluated by comparing the entire OS curves by means of the log-rank test.

The independent prognostic value of variables will be analyzed using the Cox model. The year of diagnosis will be included as a continuous variable in the multivariate analyses to exclude the possibility that modern medical management could influence outcome more than the treatment itself. Backward stepwise regression will be performed to identify the most powerful predictors of survival. All the probability values will be two-sided. Statistical analysis will be performed with Statistical software (Statistica 10.0, Tuxon, AZ, USA) on a unique database including clinical and pathological data on an estimated sample size of 555 patients.

ETHICAL CONSIDERATIONS AND INFORMED CONSENT

The Investigator and all study staff will ensure that the clinical study is conducted in accordance with good clinical practice and institutional requirements, including those for subject privacy, Ethics Committee approval and record retention, and with the Declaration of Helsinki (revised October 2008) and in compliance with principles defined in the Determinazione of the Agenzia Italiana del Farmaco, dated 20 March 2008. The protocol, being retrospective, will be notified to the IEC of the IRCCS San Raffaele Scientific Institute

of Milan. In the context of clinical practice, patients already provided consent to use of health data for research purposes.

PATIENT SAFETY

Given the observational retrospective nature of the study, for the patients enrolled in this study, there are no additional physical, psychological, or social adverse effects compared to the standard of care clinical practice.

FINANCE AND INSURANCE

The study is non-profit in nature.

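### The protocol promises the prevalence of MYC, BCL2 and BCL6 rearrangements in LBCL, but counts them only in treated, HIV-negative, single-centre patients with usable tissue and outcome data

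*Protocol*

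**What the plan says.** The target is stated three times without restriction. Under Objectives, secondary objective 5 is "To estimate the prevalence of MYC, BCL2 and BCL6 rearrangements/amplifications detected by FISH in LBCL"; the synopsis table repeats it. Under Therapeutic Outcome, secondary outcome 5 is "Incidence of MYC, BCL2 and BCL6 rearrangements in LBCL". The Rationale says that "this study could give important information about the real incidence and predictive value of MYC, BCL2 and BCL6 rearrangements".

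The sample is restricted in several ways. The inclusion criteria under Study Population require "Treatment with R-CHOP or other intensified polychemotherapy regimen", "Availability of adequate histopathological samples at diagnosis for FISH analysis", "Availability of clinical records and outcomes data" and "HIV sero-negativity". Under Methods, Histopathology and Immunohistochemistry, a further selection step says that "we will carefully consider only tissue blocks showing enough material to allow completion of immunohistochemistry and FISH analyses". Study Design states that there is one centre.

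**The concern.** A prevalence is a numerator over a denominator, and the denominator here is set by filters that the objective does not mention.

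- **Treatment.** Patients who died before treatment, or who were given something less, are outside the count. The Background describes HGBL as having an adverse prognosis, with median survival of no more than 12 months on standard treatment. It is therefore plausible that reaching such treatment is related to rearrangement status. The criterion makes sense for survival and response, but none for a prevalence.
- **Tissue.** A case counts only if enough material is left. The Background says that at this centre MYC FISH follows high MYC staining, and BCL2 and BCL6 FISH follow a positive MYC FISH. Past use of tissue may therefore be linked to the quantity being counted.
- **Records and HIV status.** These narrow the group further.

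At stake is what the study may conclude. A figure reported as that of LBCL would be read as applying to patients whom the study never sampled.

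**Working it through.** **1. Target against sample**

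| | Objective 5, outcome 5, Rationale | Eligibility and case selection |
|---|---|---|
| Disease | LBCL | LBCL |
| Treatment | no restriction | R-CHOP or an intensified regimen |
| Tissue | no restriction | enough for IHC and FISH |
| Records | no restriction | records and outcomes available |
| HIV status | no restriction | negative only |
| Setting | no restriction | one centre |

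The two columns differ in every row but the first. This step needs no assumption.

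**2. The plan's own figure.** There is none to reproduce. The sample size of 555 is given as an estimate, and the protocol gives no expected prevalence and no count of cases lost at any step. All inputs below other than 555 are therefore assumptions.

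**3. Sampling error at n = 555.** The Wilson 95% interval is [p + z²/(2n) ± z√(p(1−p)/n + z²/(4n²))] / (1 + z²/n), with z = 1.96.

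**4. Effect of selection.** If a share r1 of rearranged and r0 of other cases pass the filters, the observed proportion is p·r1 / (p·r1 + (1−p)·r0).

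| Assumed true p | Wilson 95% CI | r1 = r0 = 0.9 | 0.7 / 0.9 | 0.5 / 0.9 | 0.9 / 0.7 | 0.9 / 0.5 |
|---|---|---|---|---|---|---|
| 5% | 3.5 to 7.1% | 5.0% | 3.9% | 2.8% | 6.3% | 8.7% |
| 10% | 7.8 to 12.8% | 10.0% | 8.0% | 5.8% | 12.5% | 16.7% |
| 15% | 12.3 to 18.2% | 15.0% | 12.1% | 8.9% | 18.5% | 24.1% |

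(Column labels are r1 / r0.) For example, 0.10 × 0.7 / (0.10 × 0.7 + 0.90 × 0.9) = 0.07 / 0.88 = 8.0%. Equal retention gives no bias. At 5% and 10%, a contrast of 70% against 90% moves the estimate by less than the sampling error; at 15% it moves it just outside the interval. A contrast of 50% against 90% goes well outside at every p. A larger sample would not remove the shift.

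**5. Treatment filter alone.** Assume that 8% of treated patients are positive and that 20% of LBCL fall outside the treatment criterion with 12% or 16% positive. The overall figure is 0.8 × 8% + 0.2 × 12% = 8.8%, or 0.8 × 8% + 0.2 × 16% = 9.6%. A lower proportion among those excluded would move it the other way.

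**6. A tempting repair, checked.** One could admit cases without tissue if a three-gene FISH result from diagnosis is on file. By the practice in the Background, such a result exists essentially only after a positive MYC FISH, so the rule brings back positives alone. Take a true HGBL proportion of 8%, with 20% of HGBL and 10% of other cases lost for tissue:

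- no repair: 0.08 × 0.8 / (0.08 × 0.8 + 0.92 × 0.9) = 0.064 / 0.892 = 7.2%
- all lost HGBL brought back: 0.08 / (0.08 + 0.92 × 0.9) = 0.08 / 0.908 = 8.8%

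An error of −0.8 points becomes one of +0.8 points.

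**The case against.** The strongest reply has four parts.

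- **The denominator is open to view.** The protocol calls itself a retrospective single-centre series and prints its criteria, so a careful reader can see who was counted. That is true, but the objective and the outcome still name a wider population, and reports are written from those lines.
- **The Rationale is modest.** It says only that the study could inform the true incidence. In the Background that phrase contrasts FISH in all cases with FISH triggered by staining, a contrast that the study can address within its own cohort. This stands. It supports a statement about the cohort, not about LBCL.
- **Tissue is unavoidable for new FISH, and treatment is needed for survival.** Both are right. The criteria need not be dropped; the fault lies in the wording of the estimate.
- **Every magnitude is assumed.** Also right. At an assumed 8% and n = 555, the Wilson interval is about 6.0 to 10.6%, and 7.2%, 8.8% and 9.6% all lie inside it.

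A tally of exclusions may also stand in an analysis plan that is not at hand. The point does not rest on its absence, because the objective and the eligibility criteria are both fixed in the protocol.

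**Conclusion.** The stated target is wrong as written. The design delivers the proportion with rearrangements among treated, HIV-negative patients at one centre who have outcome data and evaluable tissue, and the protocol calls it the prevalence or incidence in LBCL. This follows from the text alone. Size and direction of any bias cannot be derived; if passing the filters is unrelated to rearrangement status, there is none.

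A reader might infer more: that recognised HGBL are systematically lost because their blocks are used up, so that the figure is too low and the HGBL group in the survival analysis is depleted. The documents do not support that, for these reasons:

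- No section says that any block is exhausted or that retention differs by status.
- The stepwise FISH practice is described in the present tense and is not said to cover 2000 to 2019.
- Cases with high MYC staining but negative MYC FISH also had sections cut.
- The argument does not reach BCL2 or BCL6 rearrangements in cases that never had those tests.
- The protocol accepts earlier CD10, bcl-6 and MUM-1 results and is silent on earlier FISH results; it does not forbid their use.

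Such loss is possible but not documented.

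**What to change.** 1. Restate secondary objective 5 (also in the synopsis) and secondary outcome 5 as the proportion with each rearrangement among treated, HIV-negative patients at this centre with evaluable tissue and outcome data.
2. Replace *incidence* in outcome 5, and the corresponding phrase in the Rationale, by *proportion*.
3. From the archive list, count cases excluded for treatment, for tissue and for records. Compare their MYC IHC and FISH status, where on file, with that of included cases, and use the result to give a sensitivity range for the prevalence.
4. Do not admit cases without tissue to the main estimate on historical three-gene FISH. Use such results at most in a flagged sensitivity analysis or in describing HGBL outcomes.

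The cost is a narrower claim and a small archive tally. No new assays are needed, and the eligibility criteria can stay as they are.

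### The planned response test compares treatment groups without adjustment, although at least one regimen followed risk and MYC status and the response objective is about FISH class

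*Protocol*

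**What the plan says.** Protocol, Statistical Considerations and Analysis Plan, first sentence: "Clinical characteristics and response rates of the therapeutic subgroups will be compared using the" chi-square test (printed with an alpha) or Fisher exact test, depending on sample size. The next sentence assesses factors that may affect outcome by chi-square "test and logistic regression". Further on, after the Cox model is introduced: "The year of diagnosis will be included as a continuous variable in the multivariate analyses", because modern management "could influence outcome more than the treatment itself".

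Protocol, Background, on CARMEN: this "regimen was adopted at our institution and at several Italian Centers also for the treatment of HIV-negative patients diagnosed with high-risk DLBCL", and the full indication is given as "high-risk DLBCL as well as B-cell lymphoma unclassifiable with features intermediate between DLBCL and BL with alterations of c-MYC". On testing practice at the centre: "FISH for MYC is considered when MYC expression by IHC is >40"%.

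Protocol, Objectives: secondary objective 1 is the association between FISH re-classification and response to treatment. The synopsis lists the same association as primary objective 2. Secondary objective 6 reads "To describe the main treatment patterns according to disease characteristics". Secondary objective 3 concerns FISH re-classification as support for treatment decisions and names no contrast between regimens.

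**The concern.** Two things do not fit together.

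First, the grouping variable. The only response comparison whose groups the section names is by treatment. The response objective asks about FISH class. Followed as written, the plan yields a p-value that no objective requests, and it names no response test for the question that the objectives do ask.

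Second, confounding by indication. The cohort pools patients given R-CHOP with patients given intensified regimens, and CARMEN was directed at patients with high-risk disease or c-MYC alterations. Those features overlap with what the study sets out to classify, and the Background describes HGBL as responding poorly to standard treatment. A crude test of response by regimen therefore mixes any real regimen effect with the difference in case mix. Equally effective regimens could appear to differ, and a real advantage of an intensified regimen could be masked.

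The risk of misreading is realistic. The Rationale hopes that the results will help to choose treatment, and the reason given for adjusting for year of diagnosis shows that the authors expect to read a treatment effect from these data.

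**Working it through.** **1. Grouping variable against objective**

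| Place in protocol | Grouping | Kind of statement |
|---|---|---|
| Synopsis, primary objective 2 | FISH class | association with response |
| Objectives, secondary 1 | FISH class | association with response |
| Objectives, secondary 6 | treatment patterns | description only |
| Statistical section, first sentence | therapeutic subgroups | chi-square or Fisher test of response |
| Statistical section, second sentence | not named | chi-square and logistic regression, outcome and covariates not named |

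The tested grouping in the fourth row matches none of the objectives.

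**2. Is selection into treatment documented?** Yes for CARMEN (Background). The protocol gives no assignment rule for other regimens.

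**3. Does other text adjust for it?** Year of diagnosis is the only covariate fixed in advance. It addresses era, not selection on risk or MYC status. The logistic regression sentence could cover response but does not say so.

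**4. How large could the distortion be?** The protocol gives no regimen shares, no HGBL share by regimen and no significance level, and it gives no inputs behind the figure of 555, so there is no plan figure to reproduce. The following is an illustration.

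Inputs:
- From the protocol: total 555 (statistical section); two-sided tests; response in HGBL on CARMEN 18 of 22 = 82% (Background).
- Assumed: 80 intensified and 475 R-CHOP patients (80 + 475 = 555); HGBL share p = 30-50% of the intensified group and 3% of the R-CHOP group; response 85% in other LBCL; response H = 50-82% in HGBL; the same response under both regimens within each class (no true regimen effect); 5% level.

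Formulas:
- Intensified: R_I = p × H + (1 − p) × 0.85
- R-CHOP: R_C = 0.03 × H + 0.97 × 0.85
- Crude gap: R_C − R_I = (p − 0.03) × (0.85 − H)
- Rejection probability: two-proportion test with pooled variance under the null, normal approximation, both tails

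| H | p | R_I | R_C | Gap (points) | P(reject) |
|---|---|---|---|---|---|
| 50% | 50% | 67.5% | 84.0% | 16.5 | 0.91 |
| 50% | 40% | 71.0% | 84.0% | 13.0 | 0.77 |
| 50% | 30% | 74.5% | 84.0% | 9.5 | 0.54 |
| 70% | 50% | 77.5% | 84.6% | 7.1 | 0.36 |
| 70% | 30% | 80.5% | 84.6% | 4.1 | 0.17 |
| 82% | 50% | 83.5% | 84.9% | 1.4 | 0.07 |
| 82% | 30% | 84.1% | 84.9% | 0.8 | 0.06 |

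First row in full: pooled rate = (80 × 0.675 + 475 × 0.8395)/555 = 0.816. Standard error under the null = √(0.816 × 0.184 × (1/80 + 1/475)) = 0.0468. Unpooled standard error = √(0.675 × 0.325/80 + 0.8395 × 0.1605/475) = 0.0550. Then (0.1645 − 1.96 × 0.0468)/0.0550 = 1.32, which gives 0.91.

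Within each class the regimen difference is zero by construction, so the whole crude gap in this table is case mix. The result depends mainly on H. At 82% the test behaves almost as it should; at 50% it rejects most of the time.

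**The case against.** The strongest reply has four parts.

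*The plan does contain an adjusted tool.* Logistic regression is the natural model for a binary response, the first sentence also compares baseline characteristics of the subgroups, and covariate lists are commonly left to a statistical analysis plan, which is not shown here. This stands in part: missing covariates are not the complaint. But the protocol itself fixes the grouping variable for the response test, and nothing links the logistic model to that test.

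*The size rests on assumptions.* This stands in full. The only HGBL response rate in the protocol, 82%, makes the gap about 1 point. That figure comes from 22 patients on one regimen, within a series that mixed HIV-positive and HIV-negative patients, so it does not settle the matter either. Unrecognised HGBL in the R-CHOP group, which the Background itself suspects, would narrow the contrast further.

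*Selection is documented for one regimen only, and the subgroups are undefined.* Also true. The treatments are described as anthracycline-based with or without radiotherapy, so R-CHOP against intensified is one reading among several.

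*A treatment comparison is not foreign to the study,* which calls itself pharmacological and has an objective on treatment decisions. But that objective concerns FISH class as a guide, not a contrast of regimens.

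A reader might go further and infer that any difference found would be due solely to who received which regimen, or that a falsely significant result is likely. The documents support neither. A crude difference would mix selection with any real effect, and the chance of a spurious result cannot be derived from the figures that the protocol gives.

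**Conclusion.** The point holds in this form: the protocol fixes an unadjusted test of response by treatment group, at least one regimen was given on risk or c-MYC status, and the section names no response comparison for the FISH classes that the objective concerns. The mismatch and the confounding follow from the text and need no assumption about rates.

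The size does rest on assumptions. With the 80/475 split, HGBL shares of 30-50% against 3%, 85% response in other LBCL and no true regimen effect, the crude gap is about 1 point (rejection about 6-7%) at an HGBL response of 82%, and up to about 16 points (rejection about 91%) at 50%.

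The change should be made, but the point does not touch the overall survival analysis. Response is secondary in the body of the protocol, although the synopsis lists it under the primary objectives.

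**What to change.** Reword the first sentence of the statistical section so that:
- the inferential comparison of response is by FISH class, stratified by or adjusted for regimen, stage or baseline risk, and year of diagnosis;
- response by regimen is reported descriptively within FISH class, in line with secondary objective 6;
- any contrast between regimens is adjusted and labelled exploratory;
- the logistic regression in the second sentence is tied explicitly to response.

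No new data are needed: FISH results, staging, therapeutic management and outcome are already listed under Study Variables. The costs are one fewer p-value and small cells in some FISH-by-regimen strata, where only counts may be reportable.
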